5.6 Withdrawal of Subjects

For Aim 2, there are no consequences for withdrawing from this study. Subjects who wish to withdraw may do so at any time. We will keep any data collected up to the time of withdrawal. Withdrawal will be documented in REDCap.

5.7 Study Evaluations

For Aim 1, using national VA electronic health record data from VINCI-CDW, we will obtain the results of all nasopharyngeal or oropharyngeal swabs performed for SARS-CoV-2 PCR at the time of data abstraction and identify positive (detected) versus negative results.

Potential predictor variables will be extracted as of the time of testing for SARS-CoV-2 (for risk factors/prediction of hospitalization) and also as of the time of hospitalization (for risk factors/prediction of ICU admission, mechanical ventilation or death).

Using VINCI-CDW data, we will identify the following potential predictors/risk factors which are suspected to be associated with adverse outcomes in COVID-19:

Demographic factors: age, race, ethnicity, sex, socioeconomic status (including data from USVETS),

VA consolidated community care datasets (that track use of non-VA care paid for by the VA through the FEE basis file and the Patient Integrity Tool - PIT)

Case management/care coordination (VA Consult Toolbox)

Vital signs: temperature, blood pressure, heart rate and oxygen saturation, CAN score

Geographic factors: state, county, rural/urban, geocoded home address and associated ambient air pollution, distance to VA primary care and hospital

Comorbidities: diabetes, hypertension, COPD, asthma, history of solid organ transplantation, chronic kidney disease, cirrhosis, obesity (BMI), congestive heart failure, stroke, cardiovascular disease, HIV.

Severity of illness: Measured using variables used to calculate the VA case severity index.¹⁴

Co-infection with other viral or bacterial pathogens: influenza A or B, respiratory syncytial virus, bacterial co-infection.

Laboratory tests: CBC with differential, low lymphocyte count and high neutrophil to lymphocyte ratio (implicated in early studies as predictor), comprehensive metabolic panel [electrolytes and liver function tests], albumin (low albumin implicated as adverse predictor), brain natriuretic peptide,

PT/INR, CRP, pro-calcitonin, magnesium, troponin and IL-6 (if available, implicated as marker of cytokine storm).

Medications that may worsen outcomes: immunosuppressives, immunomodulators, corticosteroids, angiotensin converting enzyme inhibitors (ACE-I), angiotensin receptor blockers (ARB), non-steroidal anti-inflammatory drugs (NSAIDS) and thiazolidinediones which may increase the ability of the virus to enter the cells by increasing the expression of ACE2 receptors.

Supportive medications: vasopressors, inotropes, antibiotics.

Medications potentially used to treat COVID-19: remdesivir (antiviral), tocilizumab (anti-IL-6), lopinavir/ritonavir, chloroquine/hydroxychloroquine, azithromycin, ribavirin, interferon-alpha.

We will also identify receipt of imaging studies (e.g., chest X-rays and CT and MRI scans), echocardiograms, EKGs and pulmonary function tests and their finding can be extracted from the associated text integration utility (TIUs) notes in CDW

Potential long-term health outcomes we propose to extract from CDW:

Pulmonary: home O2 prescription, abnormalities in pulmonary function tests, abnormal radiographic findings on chest imaging, persistent symptoms (dyspnea, cough), development of fibrotic lung disease, bronchiectasis, and pulmonary vascular disease.

Renal: hospitalized acute kidney injury, development/worsening of chronic kidney disease, initiation of acute or long-term dialysis.

Cardiovascular: new onset or worsening hypertension, heart failure, cardiac arrest, sudden cardiac death, myocardial infarction, acute coronary syndrome, abnormal EKG or echocardiography findings, atrial fibrillation, myocarditis, hypercoagulability, DVT, pulmonary embolism and requirement for cardiac interventions (e.g., CPR, LVAD, cardioversion, coronary revascularization).

Neurological: hemorrhagic or ischemic stroke, acute neuropathy or encephalopathy, new onset seizure, rapidly progressive muscle weakness, meningoencephalitis, and acute myelitis.

Mental Health: newly diagnosed or worsening depressive disorders, depression screening, PTSD and other anxiety and mood disorders, serious mental illness (schizophrenia, bipolar, and/or psychosis), suicidal ideation, suicidal attempts, deaths due to suicide, and homelessness.

Substance Use: Presence of or treatments for unhealthy alcohol use, alcohol use disorder, tobacco use, stimulant use disorder (amphetamine and/or cocaine), opioid use disorders, and other drug use disorders (cannabis, hallucinogens and/or sedatives).

Functional Status and Pain: development of frailty or functional impairment (e.g., injurious falls, wheelchair use), cognitive impairment (dementia, delirium, memory clinic visits, prescriptions for anticholinergic agents) and reduced independence (e.g., inpatient rehabilitation, skilled nursing facility care, skilled home care and home-based primary care referrals) or new diagnoses of headache, joint pain, fibromyalgia, and chronic fatigue, as well as increase in number of comorbidities.

Text Integration utilities (TIU) notes: to support more details qualitative and quantitative analysis of the electronic health record, we will search text and develop natural language processing (NLP) algorithms using the VISA search tool within VINCI to study the content of documentation in the VA-wide electronic health records of cohort members. This will allow us to provide a rich description of the content of notes and create variables not available in structured data sources including information documentation related to care processes and interactions with the health care system. In order to understand the clinical context of the content of TIU notes, we will need to have access to the specialty/discipline and clinical role of the authors of clinical notes. While we will present extracts from the electronic health record in presentations and manuscripts, the names (e.g., patients, family members, clinicians, medical centers) and dates that appear in TIU notes will be removed from any materials presented or published outside the study team so that individual quotations cannot be traced to patients, providers or other individuals. In some instances, we will indicate the season (spring, summer, winter and fall) of the year that particular quotations appeared in patients' electronic health records so that quotations can be situated in the context of the evolving pandemic but will not record actual dates.

Medicare, Medicaid and USRDS linked Medicare data

We will obtain Medicare, Medicaid and USRDS linked Medicare enrollment, claims and survey data for 2018 through the most current year available through VIReC for all Veterans included in our SARS-CoV-2 treatment and comparison groups.

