A driving finding in VA research for the last decade has been that there is unequal and incomplete access to the benefits of VA care. EHR data by definition are only available for Veterans who have accessed care in the VA, including VA community-based care and contracted care. Other Administrative data (e.g., claims data for Medicare, Medicaid) are not available in real-time, given our dependency on other entities (i.e., CMS and VIReC) for production and linkage. Further, many important measures are not systematically ascertained or entered into the EHR in a uniform fashion for all patients. Therefore, prospective primary data collection from Veterans is necessary to define measures that are poorly captured in the VA EHR including care received at non-VA sites, caregiving receipt, disability, and employment/role function and financial toxicity, and unmet care needs in order to ensure the relevance of the work being done here. In general, we will seek to survey Veterans at 12, 18, 24, 30, and 36 months after their initial SARS-CoV-2 infection, enrolling new patients as the epidemic continues, and following patients longitudinally. The key variables of interest from new survey data for the LTO are shown in Table 2 below.

Concept	Instrument	# of items (Approx)			
Activity + Quality of Life	Activities of Daily Living (ADL) and Instrumental Activities of Daily Living (IADL); EQ-5D-5L	18			
Participation	Life Space Mobility	9+			
Employment	Health and Retirement Study's Job Status Form	1			
Financial Toxicity	NHLBI COVID-19 Financial Toxicity scale	10			
Mental Health	PHQ-9 Depression Symptoms scale	9			
Unmet Need	PROMISE instrumental support	4			
Non-VA Healthcare	VIREC Utilization Measures	2			
Fatigue + Symptoms	PROMIS Fatigue Short Form 7a; open-ended questions	9			

Aim 2 Study Population: The population of Veterans eligible for random sampling into the survey will be the same as those eligible for inclusion in Aim 1. Therefore, all data from Aim 1 will be linkable to survey responses via a cross walk.

Cases: Our primary case definition are Veterans infected with SARS-CoV-2, as defined by the standard locally available test at the time of their infection, and identified within the COVID-NST. We will restrict to Veterans seeking primary care in VA. Viral infection index date will be defined as the date of sample collection for each

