5.8 Data Analysis

For Aim 1, the data analysis team will consist of [name], [name], [name], [name] and [name]. [name] will abstract the analytic variable from VINCI-CDW. [name], the biostatistician will work closely with [name] and [name] to create the analytic models

Approach: We will use a combination of traditional epidemiologic studies and machine learning algorithms to determine the long-term, multi-systemic and functional adverse outcomes and/or syndromes related to SARS-CoV-2.

Comparison Groups: We will compare the incidence of long-term outcomes in infected and uninfected Veterans, before vs. after the pandemic and in other potentially informative control groups (e.g. untested Veterans, flu-infected patients.¹⁵)

Unsupervised Machine Learning (ML) Algorithms: We will use ML algorithms to reveal unexpected clusters or patterns of long-term outcomes, which can then be used to generated hypothesis to be tested in more focused statistical analyses. Unsupervised ML analyses will be executed at 6-monthly sequential time points because we anticipate that patterns of long-term complications may vary depending on time since infection.

Regression Analyses: We will build multivariable models (e.g., logit, generalized linear and time to event models) to evaluate associations between SARS-CoV-2 infection and the development of specific long-term outcomes that are either suspected *a priori* (see list below) or suggested by the results of unsupervised analyses. As appropriate, we will also consider approaches such as propensity score matching and instrumental variable analysis to account for measured and unmeasured confounding, respectively.

Adverse Outcomes: We will evaluate outcomes of mortality, hospitalization, readmission, healthcare utilization and costs, days in the community as well as the organ-specific outcomes listed above.

Aim 2 data analyses are described in the study methods.

6. Reporting

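### Aim 1 compares abnormal test findings by infection status with no provision for unequal testing, so the risk ratio mixes a COVID effect with testing intensity

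*Protocol*

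**What the plan says.** Aim 1 is a retrospective records study without patient contact (Protocol 5.1), so the study schedules no tests. Section 5.7 introduces its outcome list with "Potential long-term health outcomes we propose to extract from CDW". The pulmonary entry includes "abnormalities in pulmonary function tests, abnormal radiographic findings on chest imaging" and the cardiovascular entry includes "abnormal EKG or echocardiography findings". Just before that list the section says "We will also identify receipt of imaging studies (e.g., chest X-rays and CT and MRI scans), echocardiograms, EKGs and pulmonary function tests", and that the results can be drawn from clinical notes. It gives no time window for this and no use of test receipt in the analysis.

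Section 5.8 states "We will compare the incidence of long-term outcomes in infected and uninfected Veterans". It adds a before-and-after-pandemic comparison and further possible control groups, for example "untested Veterans, flu-infected patients". Its adverse-outcomes paragraph brings in the organ-specific list from 5.7. The only bias-control methods it names, to be considered where suitable, are "propensity score matching and instrumental variable analysis to account for measured and unmeasured confounding, respectively".

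For the four test-based outcome types (lung function, chest imaging, EKG, echocardiography) neither document states a denominator, a testing window, a rule on earlier tests or a method for unequal testing. The SAP covers only the Aim 2 survey measure of daily-activity limitations.

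**The concern.** If infection changes how often Veterans are sent for these tests, the recorded incidence changes even when the underlying abnormality does not. This is detection bias rather than confounding. The testing at issue comes after exposure and may be caused by it, so balancing groups on index-date characteristics does not equalise it.

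At stake is Objective 1 of Aim 1: a long-standing or incidental abnormality could be reported as a long-term effect of infection, or a real effect could be hidden. A large sample gives no protection, because it makes a biased contrast precise.

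**Working it through.** The documents give no testing rate, abnormality rate, power or effect size for these outcomes, so there is no planned figure to reproduce. All rates below are assumptions.

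**Identity.** For each group, observed incidence = P(abnormal) × P(tested | abnormal). Dividing infected by uninfected:

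observed RR = true RR × [P(tested | abnormal, infected) ÷ P(tested | abnormal, uninfected)].

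**No true effect, testing unrelated to abnormality.** Let prevalence be p in both groups. With 30% v 20% tested, RR = 0.30p ÷ 0.20p = 1.5 for any p. With 20% v 10%, RR = 2.0.

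**True RR of 1.5.**
- Testing ratio 0.7: 1.5 × 0.7 = 1.05.
- Testing ratio 1.0: 1.5.
- Testing ratio 2.0: 1.5 × 2.0 = 3.0.

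The bias can therefore run either way.

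**Overall ordering is not the quantity that matters.** Take p = 10% in both groups and 90% of abnormal Veterans tested in both. Let 30% of infected and 10% of uninfected Veterans without the abnormality be tested.
- Overall testing, infected: 0.1 × 0.9 + 0.9 × 0.3 = 36%.
- Overall testing, uninfected: 0.1 × 0.9 + 0.9 × 0.1 = 18%.
- Observed incidence: 0.1 × 0.9 = 9% in each group, so RR = 1.0 despite twice the testing.

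**Restricting to tested Veterans is not a cure.** In that example the proportions abnormal among the tested are 0.09 ÷ 0.36 = 25% and 0.09 ÷ 0.18 = 50%, giving RR 0.50 with no true effect. Two other null scenarios, also at p = 10%:

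| Tested if abnormal / if not, infected | Same, uninfected | RR, all Veterans | RR, tested only |
|---|---|---|---|
| 50% / 25% | 30% / 8% | 0.050 ÷ 0.030 = 1.67 | (0.050 ÷ 0.275) ÷ (0.030 ÷ 0.102) = 0.62 |
| 60% / 30% | 40% / 5% | 0.060 ÷ 0.040 = 1.5 | (0.060 ÷ 0.330) ÷ (0.040 ÷ 0.085) = 0.39 |

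When symptoms direct testing, the tested-only comparison can err in the opposite direction.

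**Would a spurious difference be declared significant?** With p = 10% and 30% v 20% tested, the recorded incidences are 3% and 2%. Assume two-sided alpha 0.05 and 90% power, and use the two-proportion formula with pooled variance under the null:

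n = [1.960 × √(2 × 0.025 × 0.975) + 1.282 × √(0.03 × 0.97 + 0.02 × 0.98)]² ÷ 0.01² ≈ 5,121 per group.

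Protocol section 2 puts infected Veterans at over 220,000 in early 2021, and section 5.3 puts the Aim 1 records at about 8 million. A purely testing-driven difference of this size would readily be detected.

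**The case against.** The strongest reply is that the plan is not as bare as it looks.
- Section 5.7 calls these outcomes potential ones.
- The abstract says methods for picking out new and worsening conditions are in development.
- Flu-infected controls may be followed up more like COVID survivors, and the reference attached to them (number 15) is a paper on negative controls.
- Medicare and Medicaid claims can show tests done outside VA.
- Test receipt is to be identified.

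These points show that the materials for a remedy are largely at hand. None is tied to the four outcome types or to an analysis rule, so the gap remains.

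The objection does defeat several stronger readings that a reader might infer:
- *The contrast merely measures how often tests are ordered.* That holds only with no true effect and testing unrelated to abnormality; the 36% v 18% example gives RR 1.0.
- *The bias must run away from the null.* More testing of COVID survivors is plausible, but no document shows it, and the protocol's introduction itself notes pandemic disruption of access to care.
- *Veterans without the test will be counted as outcome-free.* The plan does not say so; the denominator is unstated.
- *The sponsor has conceded this flaw.* Section 5.1 does say that "many important measures are not systematically ascertained or entered into the EHR in a uniform fashion for all patients", but it uses this to justify the Aim 2 survey and goes on to name other measures, such as caregiving, disability and non-VA care.
- *The bias passes into Objectives 2 and 4.* This is not shown: prediction of adverse outcomes of infection, and utilization and cost estimates, do not directly use these risk ratios.

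**Conclusion.** The concern holds for the four test-based outcome types only, not for the rest of the Aim 1 list. As written, the comparison estimates the true RR multiplied by a testing ratio that the plan neither measures nor adjusts for, and the named confounding methods are not directed at it. This goes beyond missing detail, because following the plan can yield a biased contrast. Size and direction cannot be stated from the documents. The figures of 1.5 (30% v 20% tested, no true effect, testing unrelated to abnormality) and 1.05 (true RR 1.5, testing ratio 0.7) are illustrations under assumed rates. It is a worthwhile, inexpensive improvement and does not invalidate Aim 1.

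**What to change.** In Protocol 5.7 and 5.8, for abnormal lung-function, chest-imaging, EKG and echocardiography findings only:

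1. Extract test receipt over the same post-index window in both groups, and report testing rates by group beside each contrast.
2. State that the all-Veteran incidence contrast will not be read on its own as a COVID effect. Rest the main causal conclusions on outcomes less dependent on surveillance testing, such as death, myocardial infarction, stroke and dialysis.
3. Keep the test-finding contrast as secondary, with three sensitivity analyses: weighted for the probability of testing, against the flu-infected comparator already named, and excluding Veterans with the same abnormality on a pre-index test. None is complete alone. Weighting needs testing to be explained by measured variables, the flu group helps only if its follow-up testing is similar, and pre-index tests were themselves selectively ordered.
4. Add a negative-control outcome that depends on testing in the same way.
5. If proportions abnormal among the tested are shown, label them descriptive and note that symptom-directed testing can bias them in the opposite direction.

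The cost is modest extra extraction and analysis. Section 5.7 plans to identify test receipt but sets no window, so post-index receipt may need to be added. The price in reporting is a more cautious interpretation of these findings.

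### Aim 1 lists anticholinergic prescriptions as a marker of cognitive impairment; as written the marker is not valid, and it may be a slip for cholinesterase inhibitors

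*Protocol*

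**What the plan says.** The protocol's section 5.7 (Study Evaluations) introduces a list of "Potential long-term health outcomes we propose to extract from CDW". Under Functional Status and Pain, one entry reads "cognitive impairment (dementia, delirium, memory clinic visits, prescriptions for anticholinergic agents". The prescription therefore stands among the outcome markers, not the covariates. The same section has a separate list of medications that may worsen outcomes, and anticholinergics are not in it.

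The Pulmonary entry of the outcome list includes "persistent symptoms (dyspnea, cough), development of fibrotic lung disease, bronchiectasis, and pulmonary vascular disease". Chronic airway disease also appears among the potential predictors ("Comorbidities: diabetes, hypertension, COPD, asthma").

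Section 5.8 (Data Analysis) says "We will compare the incidence of long-term outcomes in infected and uninfected Veterans". It plans regression models to "evaluate associations between SARS-CoV-2 infection and the development of specific long-term outcomes", and its Adverse Outcomes paragraph takes in general outcomes "as well as the organ-specific outcomes listed above". That last phrase could be read as leaving out a functional outcome such as cognition. However, the Approach paragraph of 5.8 and the first Aim 1 objective both name functional adverse outcomes, so cognition is in scope.

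Neither document restricts the prescription marker by drug, route, indication, new use or supporting diagnosis. Neither says how the four markers combine, and neither plans a validation of the outcome.

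**The concern.** Elsewhere in the section 5.7 outcome list a treatment stands for the condition it treats: home oxygen for lung disease, and treatments for substance use disorders. On that logic the cognitive entry should name drugs given because of cognitive impairment. Anticholinergics are not such drugs. Their usual indications are airway disease, bladder symptoms and other conditions, and they can cause cognitive impairment. Cholinesterase inhibitors, which are prescribed in dementia, have the opposite action and a similar name. This is general pharmacology; the documents do not discuss it.

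Two things are at stake. One is the comparison of cognitive impairment between infected and uninfected Veterans. The other is any risk model for that outcome under the second Aim 1 objective, which could learn predictors of airway or bladder treatment instead of cognitive decline. Because the protocol lists respiratory symptoms and lung disease as possible sequelae of infection, prescribing could plausibly differ between the groups, and the misclassification would then differ too. A large health-record sample makes such an error more precise, not smaller.

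**Working it through.** **Text check.** The plan gives no rate, effect size or power for this outcome, so there is no figure to reproduce. Section 5.7 places the prescription in the description of the outcome. Section 5.8 offers multivariable models, propensity score matching and instrumental variables. These address confounding and do not correct a misclassified outcome. The natural language processing work in 5.7 is not tied to this marker.

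**Illustration 1: simple sum.** Every input is assumed, as is the rule that any single marker makes a case.

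- p = true new cognitive impairment in comparators, 0.5% to 2%
- a = new anticholinergic starts in comparators for non-cognitive reasons, 2% to 8%
- r = ratio of such starts, infected to uninfected, 1.2 to 2
- R = true risk ratio (RR)

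Ignoring overlap, apparent RR = (p·R + a·r)/(p + a). This is a weighted average of the true ratio R and the prescribing ratio r. With R = 1:

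- lowest: p = 2%, a = 2%, r = 1.2 gives (2 + 2.4)/4 = 1.10
- central: p = 1%, a = 4%, r = 1.5 gives (1 + 6)/5 = 1.40
- highest: p = 0.5%, a = 8%, r = 2 gives (0.5 + 16)/8.5 = 1.94
- equal prescribing: r = 1 gives 1.00 for every p and a

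The share of flagged comparators who are not cognitive cases is a/(p + a), from 2/4 = 50% to 8/8.5 = 94%.

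**Illustration 2: overlap allowed.** Let c be true cognitive incidence in comparators, with prescribing independent of it. Then P(flagged) = 1 − (1 − c)(1 − a). For a true RR of 1.5, c in the infected group is multiplied by 1.5. All rates are again assumed.

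| c | prescribing, uninfected → infected | RR seen if true RR is 1.0 | RR seen if true RR is 1.5 |
|---|---|---|---|
| 1% | 2% → 2% | 1.00 | 1.16 |
| 3% | 2% → 2% | 1.00 | 1.30 |
| 5% | 2% → 2% | 1.00 | 1.36 |
| 5% | 2% → 3% | 1.14 | 1.49 |
| 3% | 2% → 4% | 1.39 | 1.68 |
| 1% | 5% → 10% | 1.83 | 1.91 |

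For the 3%, 2% → 4% row with no true effect, the flagged proportions are 1 − 0.97 × 0.98 = 4.94% and 1 − 0.97 × 0.96 = 6.88%. Their ratio is 1.39, and 3/6.88 = 44% of flagged infected Veterans are true cases. Over c of 1%, 3% and 5%, comparator prescribing of 2% or 5%, and ratios of 1.5 and 2, a true RR of 1.0 appears as 1.14 to 1.83.

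**Reading.** The observed ratio is pulled toward the prescribing ratio. It is diluted when r is below the true ratio, inflated when r is above it, and nearly unchanged when the two happen to agree.

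**The case against.** The best defence is that section 5.7 is a menu, not an algorithm. Its heading calls the outcomes potential. Nothing says that the four items form a composite or that one alone makes a case. They could be extracted as separate variables, or a later code list could require a diagnosis. This stands, and it makes the misclassification conditional. It does not make the marker valid, because neither document supplies such a rule.

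A reader might infer that the analysis will count respiratory treatment as cognitive decline and so overstate the effect of COVID-19. The documents do not support that. They contain no any-marker rule and no prescribing rate for either group. Listing dyspnea and cough as potential outcomes does not establish a prescribing ratio above 1, and at equal prescribing the error dilutes a true effect.

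There are also partial mitigations. Adjusting or matching on COPD and asthma could reduce differences due to pre-existing lung disease, and the flu-infected comparison group in 5.8 could reduce a difference common to respiratory infections. Neither makes the marker specific, and adjustment for baseline disease does not remove prescribing that infection itself causes. They do weaken the upper end of a crude range.

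Finally, a Veteran started on a cholinesterase inhibitor would be missed only if no dementia, delirium or memory-clinic record existed. How often that happens is unknown.

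**Conclusion.** The definition is wrong as written: an anticholinergic prescription is not evidence of cognitive impairment, and nothing in the documents narrows it to something that is. The entry may be a slip for cholinesterase inhibitors, but the documents cannot settle the intent.

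The direction and size of any bias are not established. They depend on an any-marker rule and on prescribing rates that the plan does not give. The range of 1.10 to 1.94 for a true risk ratio of 1.0 shows only what could happen with prescribing 1.2 to 2 times higher in infected Veterans. At equal prescribing that ratio stays at 1.0, and in the second illustration a true 1.5 falls to between 1.16 and 1.36.

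The reach is one potential Aim 1 health-record outcome and any model built on it. A reader might take this as a threat to the study's main result, but the SAP's primary outcome is a self-reported IADL count from the survey, which does not use the marker. Severity is moderate.

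**What to change.** In section 5.7, remove anticholinergic prescriptions from the cognitive outcome. If drugs given for dementia were intended, replace the entry with new prescriptions for cholinesterase inhibitors or memantine. In either case, state how the remaining markers combine into a case. If a drug marker is kept, also give the drug list and the new-use rule. Recheck any cognitive outcome already extracted under the present wording. Recording baseline anticholinergic use as a covariate is a reasonable option but not essential.

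The cost is a short protocol edit and a small change to the CDW extraction. The number of counted cognitive events will change. Removal alone can only lower it, while a replacement also adds events, so the net direction is not known in advance.
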